9.4.10 Metabolomics

Blood and bone marrow supernatant samples will be sent to Metabolon for quantification using the Global Metabolomic Platform, which consists of four independent methods: ultrahigh performance liquid chromatography/tandem mass spectrometry (UHLC-MS/MS) with positive ion mode electrospray ionization, UPLC-MS/MS with negative ion mode electrospray ionization, and UPLC-MS/MS polar platform (negative ionization).⁶⁵ LC-MS will be performed on a Waters ACQUITY ultra-performance liquid chromatography (UPLC) and a Thermo Scientific Q-Exactive high resolution/accurate mass spectrometer interfaced with a heated electrospray ionization (HESI-II) source and Orbitrap mass analyzer operated at 35,000 mass resolution. All analytes will undergo quality control and curation processes, which are designed to ensure accurate, consistent

identification, and to minimize system artifacts, mis-assignments, and background noise.⁶⁵ Library matches for each compound will be verified for each sample. It is notable that the median intraclass correlations between duplicate samples on Metabolon's platform has been shown to be 0.96 (25th – 75th percentile: 0.82–0.99), and the average coefficient of variation across all named metabolites has been shown to be 0.16 (25th – 75th percentile: 0.06–0.20).⁶⁶

Metabolite features will be analyzed as measures of peak areas, which are proportional to feature concentration and can be compared for any given metabolite. The metabolite variables will be standardized to a mean of 0 and standard deviation of 1.

9.4.11 Longer-Term Benefit

It is notable that the vast majority of interventions investigated in clinical trials have involved aggressive pharmacologic agents. The proposed trial is the first to examine preliminary evidence of efficacy that metformin is a low-risk strategy to prevent progression in this population of higher-risk MGUS and low-risk SMM patients. Although we are powered to detect small but clinically relevant between group differences in M-protein concentrations from baseline to six months, we acknowledge the possibility that a six-month treatment period is too short in some patients to demonstrate a clinical benefit. To maximize the learning opportunity but maintain the rigor of the trial's short-term primary endpoints, we will allow participants to become unblinded after the primary outcome assessments are complete and participants randomized to the metformin arm of the study will be invited to continue to take metformin for an additional six months.

We will descriptively report the number of participants randomized to the metformin arm who wish to continue taking metformin, which will provide an assessment of participant's willingness to take metformin for longer-term risk-reduction. In addition, we will utilize well-established measures of response to therapy using a modified version of the International Myeloma Working Group Response Criteria defined below, as well as mass spectrometry-based estimates of minimal residual disease.

Response	Criteria for Response
Complete Response (CR)	
Negative immunofixation on the serum and $\leq 5\%$ plasma cells in bone marrow (if performed clinically), or normalization of serum free light chain ratio if followed by serum free light chain. Normalization is defined as the serum free light chain ratio being within the normal range. If the serum free light chain ratio is not within the normal range, but the individual kappa and lambda light chain values are within normal range, this may be considered CR.

Very Good Partial Response	
Serum M-protein detectable by immunofixation but not on electrophoresis or 90% or greater reduction in serum M-protein.

(VGPR)	
Partial Response (PR)	
$\geq 50\%$ reduction of serum M-protein.
 
If only measurable parameter is serum immunoglobulins free light chain (FLC), EITHER of the following changes qualify as partial response:
 
 - A 50% decrease in the difference between involved and uninvolved FLC levels; OR - A 50% decrease in the level of involved FLC AND a 50% decrease (normalization) in the ratio of involved/uninvolved FLC
Stable Disease (SD)	Not meeting criteria for CR, VGPR, PR or progressive disease.
Progressive Disease (PD)	
$> 25\%$ increase of serum M-protein (which must also be an absolute increase of ≥ 0.5 g/dL). PD is also measured by an absolute increase in bone marrow plasma cells $> 10\%$. If only measurable parameter is serum immunoglobulins free light (FLC), either of the following qualify as progression:
 
 - 50% increase in the difference between involved and uninvolved FLC levels from the lowest response level, which must also be an absolute increase of at least 10 mg/dL; OR - 50% increase in the level of involved FLC AND a 50% increase in the ratio of involved/uninvolved FLC from the lowest response level.

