3. PARTICIPANT SELECTION

3.1 Eligibility Criteria

3.1.1 Diagnosed with high-risk MGUS or low-risk SMM⁶³ defined below:

Higher-Risk MGUS: bone marrow plasma cell concentration <10%# AND either serum M-protein level ≥ 1.5 g/dL to <3 g/dL, abnormal free light-chain (FLC) ratio (<0.26 or >1.65), or IgA MGUS.

Note: individuals with an abnormal FLC ratio that are classified as light-chain only are eligible. Light-chain only patients are defined as complete loss of immunoglobulin heavy-chain, accompanied by abnormal FLC ratio with an increased level of the appropriate involved light-chain (increased kappa FLC in patient with ratio >1.65, and increased lambda FLC in patients with ratio <0.26).

Low-Risk Smoldering Myeloma: bone marrow plasma cells $\geq 10\%$ # with the absence of additional high-risk features, which are further defined in the exclusion criteria (3.2.1)⁶⁴

#A new bone marrow biopsy is preferred for plasma cell determination at screening; however, determination of eligibility can be made from most recent bone marrow biopsy performed as long as it was within 2 years of enrollment.

3.1.2 Absence of evidence of CRAB criteria* or new criteria of active MM or active WM which including the following (note if one or more criteria has not been evaluated (e.g., no MRI), the criteria for active MM or WM for that feature is considered unmet):

- Increased calcium levels (corrected serum calcium >0.25 mmol/dL above the upper limit of normal or >0.275 mmol/dL) related to MM
- Renal insufficiency (attributable to MM)

- Anemia (Hb 2g/dL below the lower limit of normal or <10g/dL) related to MM
- Bone lesions (lytic lesions or generalized osteoporosis with compression fractures)
- Bone marrow plasma cells $\geq 60\%$
- Serum involved/uninvolved FLC ratio ≥ 100 , provided the absolute level of the involved free light chain is at least 100 mg/L and repeated twice (light chain smoldering myeloma as described in section 2.4 is not an exclusion criteria).
- MRI with two or more focal lesion that is at least 5 mm or greater in size
- Hyperviscosity symptoms per WM guidelines for symptomatic WM

**Participants with CRAB criteria that are attributable to conditions other than the disease under study may be eligible*

3.1.3 At least 18 years of age.

3.1.4 Eastern Cooperative Oncology Group (ECOG) performance status of 0, 1, or 2.

3.1.5 The following laboratory values obtained prior to the first dose of study drug/placebo:

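### In the modified IMWG table, complete response by free-light-chain (FLC) ratio can need a smaller change than partial response, so a patient who enters just past the cut-off can be scored a complete responder by measurement noise.

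*Combined protocol and SAP*

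**What the plan says.** **Entry.** Section 3.1.1 admits higher-risk MGUS on any of several features, one being "abnormal free light-chain (FLC) ratio (<0.26 or >1.65), or IgA MGUS". It adds that "individuals with an abnormal FLC ratio that are classified as light-chain only are eligible", provided the involved chain is also raised.

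**CR.** In the Section 9.4.11 table, negative immunofixation with a marrow condition is one route. The alternative is "normalization of serum free light chain ratio if followed by serum free light chain". The row continues: "Normalization is defined as the serum free light chain ratio being within the normal range". It prints no limits and states no minimum fall, absolute change or repeat sample. A further clause covers a ratio that is still abnormal: "but the individual kappa and lambda light chain values are within normal range, this may be considered CR".

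**PR.** This lower category applies its FLC rule only where FLC is the sole measurable parameter. The first qualifying change is "A 50% decrease in the difference between involved and uninvolved FLC levels; OR". The alternative is a 50% fall in both the involved chain and the ratio.

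**Safeguards on other FLC rules.** Progression by FLC difference carries a floor, "which must also be an absolute increase of at least 10 mg/dL; OR". The ratio ≥100 criterion in Section 3.1.2 applies "provided the absolute level of the involved free light chain is at least 100 mg/L and repeated twice".

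**Sampling and use.** The Section 10 calendars schedule FLC at baseline and End of Study for all randomized participants, and once more at the end of the extension. Section 12.7 applies the response criteria to participants who extend metformin, reports depth and duration of response, and calls that analysis exploratory.

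**The concern.** CR is the top category, yet its FLC route asks only that the ratio lie on the normal side of a line. If that line is also the entry line, a patient who entered slightly beyond it needs only a trivial change to be called a complete responder. A patient with a much larger fall can remain stable disease. A depth-of-response summary built on such a scale is wrong for some patients. All extenders take metformin, so the 12-month readout has no concurrent control to show how many crossings are chance. In a small group, one or two such CRs could dominate the description.

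**Working it through.** **Plan's own figure.** The plan states none for the CR rule. Its one design calculation, the primary-endpoint power in Section 12.1, reproduces: 2(1.960+0.842)² × 0.99²/0.73² = 28.9, so 29 per arm against the planned 30. It plays no part below.

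**Inputs.** From the documents: entry limits 0.26 and 1.65, and the 50% PR rule. Assumed, because the documents do not give them: within-patient CV of the ratio, the distribution of true ratios, kappa as the involved chain, and a constant uninvolved chain.

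**Step 1: ordering, with no noise assumption.** Let r be the entry ratio (kappa involved) and measure in units of the uninvolved chain, so the FLC difference is r − 1.
- Fall in ratio needed for CR: 1 − 1.65/r. This is 0.6% from 1.66, 2.9% from 1.70, 8.3% from 1.80 and 17.5% from 2.00.
- Fall in the difference at that point: 1 − 0.65/(r − 1). It equals 50% at r = 1 + 2 × 0.65 = 2.30. Below 2.30, CR can be reached without the PR fall.
- Lambda involved: 1/0.26 = 3.846, and 1 + 2 × 2.846 = 6.69, so the band is 0.149 to 0.26.
- The second PR limb does not rescue this. With the uninvolved chain constant it means halving the ratio, which is stricter than halving the difference.

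| Change in ratio | Fall in ratio | Fall in difference | Category |
|---|---|---|---|
| 1.70 to 1.60 | 0.10/1.70 = 6% | 0.10/0.70 = 14% | CR |
| 20 to 11 | 9/20 = 45% | 9/19 = 47% | Stable disease |

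**Step 2: chance CR at a given observed entry ratio.** No true change, log-normal error with s = √ln(1+CV²) at both visits, flat prior on the true ratio: P = Φ[ln(1.65/r)/(s√2)]. For r = 1.70 and CV 10%, s = 0.0998 and P = Φ(−0.0299/0.141) = 42%.

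| Entry ratio | CV 10% | CV 20% | CV 30% |
|---|---|---|---|
| 1.70 | 42% | 46% | 47% |
| 1.80 | 27% | 38% | 42% |
| 2.00 | 9% | 25% | 32% |
| 2.50 | 0.2% | 7% | 16% |
| 3.00 | 0.0% | 2% | 8% |

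The risk is high near the line and fades with distance from it.

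**Step 3: averaged over entrants, by simulation.** True ratio log-normal with median 1.5 and log-SD 0.8; entry if the observed ratio exceeds 1.65 (entrant median about 2.7-2.8); one follow-up visit; no true change.

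| CR rule | CV 10% | CV 20% | CV 30% |
|---|---|---|---|
| As written | 6.1% | 11.9% | 17.1% |
| Plus existing PR difference limb | 1.0% | 7.4% | 13.7% |
| Plus 50% fall in the ratio | 0.0% | 0.5% | 4.1% |

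With entrant medians of about 3.3 to 4.0, the as-written figures fall to about 3-4/6-8/9-12%.

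**Step 4: which repair works.** The PR difference limb is weak near the line. From 1.70 the difference halves at 1.35, only a 0.35/1.70 = 21% fall in the ratio. A repeat sample alone is also weak: at entry ratio 1.70, chance CR drops only to 25/29/30%.

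**The case against.** **Exploratory use.** No test or decision rests on this table, the primary M-protein comparison is untouched, and mass spectrometry is a second assessment. This stands and limits the weight of the point.

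**Assumed inputs and unknown denominator.** CV, ratio distribution and kappa involvement are all assumed. The percentages are per FLC-abnormal entrant, a subset of about 30 metformin participants. Light-chain-only patients must also have a raised involved chain, which the simulation ignores. This stands: no expected count of false CRs can be given. Step 1 is free of the noise assumptions.

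**Matching cut-offs.** A reader might infer that the plan states 0.26-1.65 as the CR range. It does not; the match is inferred because these are the only limits the documents print for an abnormal ratio.

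**Unchanged M-protein scored as CR.** A reader might infer that, because FLC is measured in everyone, any participant with an unchanged M-protein could be CR through FLC. The documents do not support this. The row is restricted to patients followed by FLC, and being measured is not the same as being followed. The restriction is undefined, so it needs clarifying.

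**No control at all.** A reader might also infer that chance crossings cannot be seen. The calendar collects FLC at baseline and six months in the placebo arm too. Only the 12-month point has no control.

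**Conclusion.** The concern holds as a flaw in one route to one response category. CR by FLC is not nested within PR. With the uninvolved chain constant, entry ratios of 1.65-2.30 (or 0.149-0.26) can reach CR without the PR fall, given that normal means the complement of the entry rule. Patients just past the line can be scored CR by noise. That is weaker than saying they generally will be: averaged over FLC-abnormal entrants, the chance at one visit is about 6/12/17% at assumed CVs of 10/20/30%, and lower if entrants sit further from the line. The clause on individually normal kappa and lambda likewise asks for no minimum change. The documents do not support extending this to the trial's primary conclusion. It is a point to consider, worth correcting because the correction is cheap.

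**What to change.** 1. In the CR row of Section 9.4.11, limit the FLC route to participants whose only measurable parameter is FLC, as PR and progression already do. State the numerical normal range. Require at least a 50% fall from baseline in the involved/uninvolved ratio as well as a normal ratio, and apply the same fall to the clause on individually normal chains. Citing the existing FLC PR criterion alone is not enough, since its difference limb leaves about 1/7/14% chance CR. It is still worth requiring in addition. If both chains rise, say from 30 and 10 to 42 and 30, the ratio falls 53% (3.0 to 1.4) but the difference only 40% (20 to 12).

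2. Score the six-month FLC by the same rule in both arms, and report the placebo CR rate beside the metformin rate.

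3. Label a CR not seen on a second routine sample as unconfirmed. After the 12-month visit, a repeat falls after study metformin has stopped, so a failed confirmation there may reflect stopping the drug.

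**Cost.** Table wording and one extra tabulation, with no new visit. There will be fewer CRs, and some will remain unconfirmed.

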12.7 Analysis of Secondary Endpoints

The secondary endpoint of this trial will be changes in a variety of biomarkers detailed in section 1.2. Changes in continuous variable outcomes will be evaluated from baseline to follow-up in the two groups using a repeated measures mixed-effects model that accounts for the correlation between baseline and follow-up measures and is generally robust to missing data. The baseline value of the dependent variable and disease subtype will be included as covariates in the regression models. Group-by-time interaction terms will be included as fixed-effects in the regression model. Model fit will be assessed using standard methods. All primary analyses will utilize stratified testing and intention-to-treat methods.⁷²

For changes in gene expression patterns, the precise methods are subject to change pending advancements in technology, but a general overview is provided below:

Paired-ended reads will be aligned against UCSC hg19 human annotation using Tophat 2.0.10; read counts for each gene will be determined using HTSeq 0.5.4. A subset of cells with more than 100,000 total reads across all genes will be selected for further analysis (70-80% of cells). To determine population average gene expression, the read counts observed in each cell will be normalized by the effective library size, determined by edgeR ‘calcNormFactors’ method. NMF-based consensus clustering will be used to cluster all single-cell RNA profiles. We will use coexpression networks-based gene prioritization tool GRAIL (<https://www.broadinstitute.org/mpg/grail/>) to select the most promising genes using gene expression signature as seeds. Cufflinks and Cuffdiff will be used to identify differentially expressed genes between the treatment arms.⁷³

Metabolite features will be analyzed as measures of peak areas, which are proportional to feature concentration and can be compared for any given metabolite. The metabolite variables will be standardized to a mean of 0 and standard deviation of 1.

For optional treatment extenders, this analysis is exploratory. We will assess the proportion of participants who are willing to take metformin for an additional 6 months. We will also evaluate response, duration of response, and depth of response according to modified IMWG criteria, or by mass spectrometry assessment.

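### Three limbs of the modified response table are states, not changes, so an eligible patient can meet VGPR or CR at baseline and be scored a responder in the metformin extension with no change

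*Combined protocol and SAP*

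**What the plan says.** **Entry (section 3.1.1).** Higher-risk MGUS requires marrow plasma cells below 10% "AND either serum M-protein level ≥ 1.5 g/dL to <3 g/dL, abnormal free light-chain (FLC) ratio (<0.26 or >1.65), or IgA MGUS". A note adds that "individuals with an abnormal FLC ratio that are classified as light-chain only are eligible", and defines them as having a raised involved light chain. Low-risk SMM requires at least 10% marrow plasma cells "with the absence of additional high-risk features, which are further defined in the exclusion criteria". Only the first MGUS route carries a lower limit for M-protein.

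**Response table (section 9.4.11).** VGPR is "Serum M-protein detectable by immunofixation but not on electrophoresis or 90% or greater reduction in serum M-protein". CR can be reached in three ways:

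- by negative serum immunofixation with no more than 5% marrow plasma cells, the marrow part applying only where a marrow is done in routine care;
- for a patient followed by FLC, by normalization of the ratio;
- or, where that ratio is abnormal, "but the individual kappa and lambda light chain values are within normal range, this may be considered CR".

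Stable disease (SD) is what remains when no other category applies.

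**Use (section 12.7).** For patients who continue metformin beyond 6 months: "We will also evaluate response, duration of response, and depth of response according to modified IMWG criteria, or by mass spectrometry assessment". The section calls this analysis exploratory. Section 5.2 restricts the extension to patients who were randomized to metformin.

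**The concern.** A response category should record improvement from where the patient began. Three limbs of this table record only what the laboratory shows on the day, and the entry criteria let in patients for whom that picture can be present before the first dose. Section 5 speaks of evaluable participants without defining the term. The table refers to FLC as the only measurable parameter without saying what makes a parameter measurable. No section says that a category already met at baseline is not a response.

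The table is the stated tool for the section 1.3 objective on how response develops over up to a year of metformin. An unchanged patient who qualifies at entry would be scored in one of the two deepest categories at the first assessment and would keep that score for as long as nothing changed. Response rate, depth and duration would all be affected. Because the extension has no placebo patients, no control rate would show how much of the apparent response was already there at entry.

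**Working it through.** The plan gives no figure for the response analysis, so there is none to reproduce. Its one design calculation (section 12.1) concerns the primary comparison, and it checks. With 30 per arm, SD 0.99 g/dL and two-sided 0.05, the standard error is 0.99 × √(2/30) = 0.256 g/dL. For 0.73 g/dL, 0.73/0.256 − 1.96 = 0.90, which gives power 81.5% (80.2% by the noncentral t). For 0.84 g/dL the power is 90.8% (89.8%). The plan states 80% and 90%. Nothing below alters this.

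**Step 1. Which limbs need a change?**

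| Limb | State at visit or change |
|---|---|
| CR, serum immunofixation negative (marrow only if done) | State |
| CR, FLC ratio normalizes | Change: a patient with an abnormal ratio at entry does not meet it then |
| CR, both light chains normal, ratio abnormal | State |
| VGPR, seen on immunofixation but not electrophoresis | State |
| VGPR, 90% fall | Change |
| PR, M-protein or FLC | Change |

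**Step 2. Apply the table literally to eligible profiles, with follow-up set equal to baseline.** The profiles are illustrative; each fits section 3.1.1.

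| Profile, unchanged from entry | Category under the table |
|---|---|
| MGUS, M-protein 1.8 g/dL | SD |
| IgA MGUS, protein seen on immunofixation only | VGPR |
| Light-chain only, immunofixation positive, electrophoresis negative | VGPR |
| SMM, 12% plasma cells, protein seen on immunofixation only | VGPR |
| Light-chain only, immunofixation negative, marrow not repeated or 4% | CR |
| Light-chain only, immunofixation negative, marrow repeated and 8% | SD |
| Heavy-chain MGUS, FLC ratio 1.8, both chains normal, followed by FLC | CR |

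The patient with a quantifiable spike is classified correctly. Five of the seven rows give VGPR or CR with no movement in disease. The two light-chain-only, immunofixation-negative rows also show that an unchanged patient can be CR or SD depending on whether a marrow was repeated.

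**Step 3. Size.** Sixty patients randomized 1:1 give at most 30 on metformin, hence at most 30 extenders. One patient who qualifies at baseline adds 1/n to the response rate:

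- n = 30: 1/30 = 3.3 percentage points
- n = 20 (assumed uptake): 1/20 = 5.0 points
- n = 15 (assumed uptake): 1/15 = 6.7 points

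The documents do not give the number of such patients, so the total cannot be computed.

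**The case against.** **The analysis is exploratory.** It has no hypothesis test, power claim or comparator. This stands and limits the weight of the point. It does not remove it: in a small uncontrolled series the response rule is the only thing that separates effect from starting position.

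**Response obviously means improvement.** The table does not leave that to be understood. It writes a reduction into PR and into the second half of VGPR, omits one from the three limbs at issue, and allows SD only when no other category is met.

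**The table was adapted for patients without M-protein.** This stands in part. CR, PR and progressive disease (PD) have FLC routes. A reader might infer that the whole table presupposes M-protein; it does not. But nothing confines a patient followed by FLC to those routes, so the immunofixation limbs stay open to light-chain-only patients.

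**The individual-chain limb is narrow.** This stands. It is permissive, applies only to patients followed by FLC, and cannot be met at entry by light-chain-only patients, whose involved chain must be raised. What is left is a heavy-chain patient with an abnormal ratio and both chains normal. The documents do not show that any will enroll.

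Three stronger readings are tempting and are not supported:

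- *Every flaw in the table favours metformin.* VGPR has no FLC route, so FLC improvement alone cannot earn it. The second FLC limb of PD has no absolute floor, so small rises can count as progression. Both work the other way.
- *Below 0.5 g/dL, M-protein must double before PD is possible.* The M-protein limb does ask for a relative "increase of serum M-protein (which must also be an absolute increase of ≥ 0.5 g/dL". But PD can also be declared on marrow plasma cells, where a marrow is done.
- *PR needs an absolute floor because PD has one.* That is a design preference; the documents do not show its absence to be an error.

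**Conclusion.** The point holds in a limited form. As written, sections 3.1.1 and 9.4.11 together allow an eligible patient to meet VGPR or CR at baseline and to be scored a responder without any change. The claim is that this can happen, not that it will happen in a known share of patients. Each such patient adds at least 3.3 percentage points to the extension response rate, and more if fewer than 30 extend.

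This rests on reading the table literally and on no unstated rule that a response must be new since baseline. It is firmest for the immunofixation-only limb of VGPR and weakest for the individual-chain limb of CR.

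A reader might go on to attach an overall figure, such as a spurious response rate of 10–20%. The documents give no proportion of patients without a quantifiable spike, and some of those patients would be followed by FLC, so no such rate can be supported. A reader might also infer that the trial's main result is compromised. It is not: the primary analysis compares M-protein between randomized arms and does not use the response table.

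**What to change.** Add to sections 9.4.11 and 12.7:

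1. Response is scored only on a parameter measurable at the pre-treatment baseline. For the electrophoresis and immunofixation criteria, that is a quantifiable M-spike. For the FLC criteria, it is a raised involved light chain with an abnormal ratio.
2. A category already met at baseline does not count as a response.
3. Patients with no measurable parameter are left out of the categorical response rate and reported separately, by change on mass spectrometry. The number evaluable is shown beside the rate.

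The cost is a few lines of text. The Study Calendar (section 10) already collects electrophoresis, immunofixation and FLC at baseline, and section 9.3 already plans mass spectrometry on all samples. No sample size or power figure changes. The one downside is a smaller number evaluable for categorical response.
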